## STUDY DESIGN

# 5.1 Overall design

A retrospective matched cohort study with Cox proportional hazards modeling will be performed to assess the risk of HZ after RZV in adults aged ≥50 YOA with RA, IBD, SLE, MS, PsO, or PsA. In the primary analysis, participants receiving a second dose of RZV (separated by >28 days after dose 1) on or after 01 January 2018 will be compared to participants with no prior RZV vaccination (i.e., unvaccinated). After identifying the sub-cohorts for each AID condition, vaccinated patients will be matched exactly to unvaccinated patients on a ratio of 1:3 by age category of 5-year increments (i.e., 50-54 age grouping) and by AID-related medication category (mutually exclusive) based on current use at the index date. Matching will be used to better control for the confounding effects and reduce bias in this observational study. The matching ratio of 1:3 is selected by optimizing the sample size and potential censoring for the unvaccinated participants due to receipt of RZV. For IBD, a vaccinated participant with UC will be matched to an unvaccinated participant with UC. The same approach will be used to match participants

219111 (EPI-ZOSTER-097 VE US DB) Protocol Final

with CD. Matching will be done with replacement. Several papers indicate that the use of replacement provides the most reliable treatment effect estimates [Bottigliengo, 2021]. Details will be described in the SAP prior to the analysis. This strategy can create better balance, which should yield estimates that are closer to the truth on average. To address additional potential confounding due to differences between vaccinated and unvaccinated cohorts, multiple covariates (Section 6.2) will be assessed and balanced across the exposure groups using propensity score matching. Unvaccinated participants will be assigned the same index date as their vaccinated counterparts.

The study will be conducted using health care encounters/claims of the Optum™ database (Section 3.1). The primary outcome is a HZ event and the primary exposure of interest is the receipt of 2 doses of RZV separated by ≥28 days after dose 1. The index date will be defined as the date of receipt of the second dose for RZV (at least 28 days after first dose) for vaccinated participants and their unvaccinated matches.

Additional secondary objectives will examine 1-dose (with the index date as the date of receipt of RZV dose 1) and 2-dose VE by age, gender, time since vaccination, time interval between two doses, and medication category, respectively. Secondary analyses will also stratify 2-dose VE by UC and CD. Analyses will be conducted separately among participants diagnosed with RA, IBD, SLE, MS, PsO, and PsA. The study period from identification of vaccinated cases to study completion will be 01 January 2018 to the first occurrence of HZ, termination of membership, death, receipt of RZV for unvaccinated participants, receipt of second dose of RZV for 1-dose cohort, receipt of ZVL, or 31 December 2021 (i.e., end of the study period).

All participants are required to have at least 3 months of follow-up time, which means the latest follow-up start date for all cohorts will be 30 September 2021, 3 months before the end of the study period (31 December 2021).

Figure 1 describes the cohort design to assess two-dose vaccine effectiveness.

[figure not shown]

Figure 1 Matched 2-dose cohort study

430 days includes the time to allow to build immunity

Age

Gender

Race/ethnicity

AID-related medications

Medical encounters

· Healthcare cost level

· Concomitant vaccinations

[figure not shown]
· Regions of U.S. residence

· Use of preventative services

· Co-morbidities

Figure 2 describes the cohort design to assess one-dose vaccine effectiveness.

Figure 2 Matched 1-dose cohort study

## 5.1.1. Rationale for retrospective matched cohort design

To assess VE, a retrospective matched cohort design will be used to compare the hazard of HZ in vaccinated participants with SLE, MS, RA, IBD (UC, CD), PsO, or PsA, respectively, who received two doses of RZV relative to unvaccinated participants who receive no RZV, using Cox proportional hazards models. A cohort design is used to evaluate the effectiveness of vaccination over time. Moreover, the potential for healthy-user bias (where vaccinated populations may more frequently have healthy behaviors) and differing characteristics among vaccinated and unvaccinated participants related to comorbidities, health status, disease activity, medications, and other factors necessitate rigorous methods to account for confounding (e.g., propensity score methods described in Section 7.6) that can be evaluated using a retrospective matched cohort design.

# 5.2 Limitations and strengths

#### 5.2.1 Limitations

Various limitations must be considered in a retrospective matched cohort study design, including confounding, bias, and misclassification.

1. Definition of the cohorts: Though the majority of the algorithms that will be used to identify participants with AIDs have demonstrated a good positive predictive value (PPV) (Section 7.5), some misclassification is expected using the validated AID-specific algorithms given the difficulty in diagnosing some AIDs (e.g., SLE, MS). In addition, some participants with well controlled AIDs may not be captured, with algorithms biasing towards a higher risk group. To improve confidence in the definitions, similar algorithms that are being used in studies that are targeting AID

219111 (EPI-ZOSTER-097 VE US DB)
Protocol Final

populations [EPI-ZOSTER-041; EPI-ZOSTER-044] will be used. These studies rely on specialists (e.g., neurologists, rheumatologists, dermatologists) consultation to provide expert opinion on the definitions of the AIDs.

- 2. Outcome misclassification: Some participants that are reported as having a HZ occurrence may not have an accurate diagnosis of HZ occurrence, which may result in a possible underestimation of VE. However, this is expected to be minimal as the detection of HZ using an ICD-10 diagnosis code for HZ (B02.xx) from hospital, emergency department, or ambulatory visit diagnoses, and dispensing for an oral antiviral (acyclovir, valacyclovir, or famciclovir) within 7 days before or after the HZ diagnosis has been used to evaluate the HZ occurrence based on the available literature [Izurieta, 2021]. Systematic differences in HZ misclassification between vaccinated and unvaccinated are not expected.
- 3. Exposure misclassification: It is possible that some participants who are reportedly unvaccinated may have received RZV prior to entering the dataset, leading to an underestimation of VE. Receipt of RZV dose 1 or 2 will be identified from administrative and claims data by means of Current Procedural Terminology (CPT) code 90750 and National Drug Code (NDC) codes 58160-828-01, 58160-829-01, 58160-819-12, 58160-828-03, 58160-829-03, and 58160-823-11 to minimize the risk of exposure misclassification. Additional codes for identification of RZV vaccination may be considered if relevant codes become available in the future.
- 4. Secular or seasonal trends in RZV use: RZV vaccination patterns may have changed during the COVID-19 pandemic. Receipt of RZV will be accurately captured in the OptumTM database, including dates of administration such that receipt of dose 1 and dose 2 are correctly ascertained. In addition, the study methods will ensure similar distributions by calendar year and season among vaccinated and unvaccinated participants and sensitivity analyses will be performed to assess if the occurrence of the COVID-19 pandemic resulted in an increase or decrease of VE. This will be further discussed in the SAP. Although in this study appropriate methodologies will be applied to statistically adjust for differences between RZV exposed participants versus RZV unexposed participants, not all potential confounders may be available in the database, and residual confounding may still be present.
- 5. Secular trends in medication use for AIDs: Newly approved therapies may be available for AIDs and may be used primarily for those with more severe disease initially. After a few years on the market, these therapies may be used in less severe disease or disease subsets. These trends may impact differences in populations and differences in the classification of disease occurrence. The study methods will ensure similar distributions by calendar year and season among vaccinated and unvaccinated participants.
- 6. Unmeasured confounding: Disease severity and disease duration may be associated with receipt of the vaccine and/or subsequent risk of HZ. However, these factors are challenging to measure in administrative claims data or may not be measured. This study assesses proxies for disease activity (such as medication use and healthcare use for disease severity) to measure confounding. Disease duration is difficult to measure as the entire medical history of a participant is not available. Confounding by indication is another potential limitation. Participants may receive RZV before initiating immunosuppressive (or more highly immunosuppressive) treatment in

219111 (EPI-ZOSTER-097 VE US DB)
Protocol Final

order to protect them from that planned treatment. This would bias the VE estimates. To address this bias, participants receiving JAK inhibitor, for example, one month after index date in the JAK inhibitor medication category will be included to account for this.

- 7. Healthy-user bias: Participants receiving RZV, or other vaccines may be healthier or have other behaviors leading to improved health compared to their unvaccinated matches. This bias may lead vaccinated participants to have lower rates of HZ in the study. The study will capture and adjust for variables related to healthy users, such as use of other vaccinations, to minimize this bias.
- 8. Duplicate health care claims: A beneficiary of OptumTM may be a beneficiary of more than one insurance product at a time or switch to a new insurance product before departing from another, resulting in duplicate health care claims and multiple lines per participant. Also, when time periods overlap, a clean link between claims and the eligibility table may be absent because multiple rows may be returned in a match. While there is a risk of this happening, the number of multiple health care claims and their impact is expected to be negligible.
- 9. Limited follow-up period: While the ability to assess durability of VE at extended time points is limited, this is an open cohort study that will allow vaccinated and unvaccinated participants to come in late or die during the follow-up period; this is not expected to impact the overall incidence rate of HZ. In addition, participants entering the cohort in early 2018 could have 4 years of follow-up.
- 10. Generalizability: The population in OptumTM have racial/ethnic diversity, and the age distribution of participants with selected AIDs in this claims database are expected to reflect the distribution nationally. The practices of care for participants with selected AIDs are expected to be largely standardized across U.S. health care systems. However, this is a claims database and only the insured and beneficiaries who have Supplementary Medicare will be included in the database.

## 5.2.2 Strengths

- Like other health claim databases, the high retention rate and stability of OptumTM membership provide an opportunity to follow participants over time and conduct long-term effectiveness studies and assess the impact of RZV vaccination in real life setting.
- 2. Optum™ is one of the largest a commercial insurance claims databases, covering inpatient, outpatient, and pharmacy claims. The database includes approximately 17-19 million annual covered lives, for a total of over 68 million unique lives over a 12-year period (1/2007 through 9/2019). Optum™ database, like other health claim databases, offers several distinct advantages over other types of data sources, including but not limited to:
  - Large sample size resulting in nationally representative sample populations covered by health insurance.
  - Complete episodes of care, including physician office visits, hospital stays, pharmacies, and other settings.

219111 (EPI-ZOSTER-097 VE US DB) Protocol Final

- Standardized diagnosis and procedure coding.
- Quarterly updates making the data from the database readily available.
- Ability to link different patient data sources i.e., subject ID with claims data related to clinical history (diagnoses, procedures) and pharmacy services.

## 6. VARIABLES

# 6.1. Exposure

The exposure of interest is the receipt of RZV (1-dose or 2 RZV doses at least 28 days apart).RZV vaccination will be identified from administrative and claims data by means of Current Procedural Terminology (CPT) code 90750 and National Drug Code (NDC) codes 58160-828-01, 58160-829-01, 58160-819-12, 58160-828-03, 58160-829-03, and 58160-823-11 (Appendix 4, Sections 13.4.3, 13.4.4, 13.4.5). Additional codes may be included for identification of RZV vaccination if relevant codes become available in the future.

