## 13.4.3. Codes to identify the use of zoster vaccine

The following Current Procedural Terminology (CPT) code will be used to retrieve Shingrix vaccinations:

Code	Description	Vaccine type
90750	Zoster (shingles) vaccine (HZV), recombinant, subunit,	Shingrix
	adjuvanted, for intramuscular use	

Codes will be updated as needed if additional codes are identified.

219111 (EPI-ZOSTER-097 VE US DB) Protocol Final

The following National Drug Codes (NDCs) codes will be used to retrieve Shingrix vaccinations:

Code	description	vaccine type
58160-082-311	Zoster vaccine recombinant, adjuvanted	Shingrix
58160-081-912	Zoster vaccine recombinant, adjuvanted	Shingrix
50090-514-700	Zoster vaccine recombinant, adjuvanted	Shingrix
58160-082-801	Varicella-zoster ge vac,2 of 2	Shingrix
50090-337-200	Zoster vaccine recombinant, adjuvanted	Shingrix
58160-082-803	Varicella-zoster ge vac,2 of 2	Shingrix

Codes will be updated as needed if additional codes are identified.

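### The RZV drug-code list in Sections 5.2.1 and 6.1 and the one in Appendix 13.4.3 agree on only four of eight codes, so doses recorded only under a discordant code can be missed

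*Protocol*

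**What the plan says.** Protocol Section 6.1 defines exposure by "Current Procedural Terminology (CPT) code 90750" and the NDCs "58160-828-01, 58160-829-01, 58160-819-12, 58160-828-03, 58160-829-03, and 58160-823-11". Section 5.2.1, item 3, gives the same six NDCs and presents them as a safeguard "to minimize the risk of exposure misclassification".

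Section 6.1 then points to "Appendix 4, Sections 13.4.3, 13.4.4, 13.4.5". In Section 13.4.3 the CPT code is the same ("The following Current Procedural Terminology (CPT) code will be used to retrieve Shingrix vaccinations"; the code listed is 90750). Its NDC table is introduced by "The following National Drug Codes (NDCs) codes will be used to retrieve Shingrix vaccinations" and contains 58160-082-311, 58160-081-912, 50090-514-700, 58160-082-801, 50090-337-200 and 58160-082-803, all labelled Shingrix.

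Both places allow changes. Section 6.1 says "Additional codes may be included for identification of RZV vaccination if relevant codes become available in the future", and Section 13.4.3 says "Codes will be updated as needed if additional codes are identified".

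**The concern.** The protocol enumerates the exposure codes twice in the text and once in the appendix, and the enumerations differ. It does not say which list governs or that the two are to be combined. Two programmers could both follow this protocol and build different cohorts.

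RZV coding drives most steps of the design:
- who is vaccinated, and the index date (Sections 1.3 and 5.1);
- the exclusion of comparators with an earlier RZV dose, and the 28-day interval check (Section 7.3);
- censoring at a comparator's first dose, at dose 2 in the 1-dose cohort and at dose 3 in the 2-dose cohort (Section 7.7).

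A missed first dose can make the second look like the first. A missed second dose can leave a 2-dose recipient in the 1-dose cohort, uncensored. If every dose is missed, a vaccinated person can serve as a comparator.

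**Working it through.** **1. Put the codes in one format.** The text codes are written 5-3-2 (10 digits) and the appendix codes 5-3-3 (11 digits). As printed, none of the six strings match. Padding the middle segment of the text codes with a leading zero (58160-828-01 becomes 58160-0828-01) and regrouping the appendix digits (58160-082-801 becomes 58160-0828-01) makes them comparable.

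| NDC, 11 digits | Sections 5.2.1 and 6.1 | Appendix 13.4.3 |
|---|---|---|
| 58160-0828-01 | yes | yes |
| 58160-0828-03 | yes | yes |
| 58160-0819-12 | yes | yes |
| 58160-0823-11 | yes | yes |
| 58160-0829-01 | yes | no |
| 58160-0829-03 | yes | no |
| 50090-5147-00 | no | yes |
| 50090-3372-00 | no | yes |

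Four codes are shared, two are in the text only and two in the appendix only. The union is 8, and each list holds 6 of the 8.

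**2. Does CPT 90750 close the gap?** Only for doses that carry it. Section 3.1 describes pharmacy dispensing records by date and NDC and lists no CPT code for them. A pharmacy-dispensed dose is therefore not necessarily caught by 90750.

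**3. Do the update clauses close it?** Section 6.1 covers codes that appear later, not codes already printed in the same document. The appendix clause is broader but sets no precedence. The cross-reference in Section 6.1 also points to 13.4.4 (influenza vaccines) and 13.4.5 (antivirals), which do not define RZV exposure.

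**4. Size for 2-dose VE.** The protocol states no figure to reproduce here. Let m be the share of comparators who are in fact fully vaccinated with the same protection. Then

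HR_obs = HR / (1 − m + m × HR).

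With HR = 0.3 (VE 70%, the highest value in Table 4) and m assumed:
- m = 2%: 0.3 / 0.986 = 0.3043, VE 69.6%
- m = 5%: 0.3 / 0.965 = 0.3109, VE 68.9%
- m = 10%: 0.3 / 0.930 = 0.3226, VE 67.7%

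**5. How many missed people would that take?** With V the 2-dose recipients in Table 3 and U the unvaccinated in Table 2, the share of 2-dose recipients missed on both doses is f = mU / (V + mU).
- IBD (V = 5865, U = 24234): m = 5% needs 1212 / 7077 = 17%; m = 10% needs 2423 / 8288 = 29%.
- MS (V = 3121, U = 20407): m = 5% needs 1020 / 4141 = 25%; m = 10% needs 2041 / 5162 = 40%.

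In the other direction, for IBD, the cohort with the largest V/U: if f is 1%, 5%, 10% or 20%, m is 0.2%, 1.3%, 2.7% or 6.1%. A true VE of 70% is then seen as 69.9%, 69.7%, 69.4% or 68.7%, and a true 50% as 49.9%, 49.7%, 49.3% or 48.4%.

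**6. Direction for 1-dose VE.** Contaminated comparators lower it. Two-dose recipients mistaken for 1-dose recipients raise it if two doses protect better, as the Medicare study cited in Section 1.1 suggests (57.7% after one dose, 68.0% after two). The net sign is not determined.

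**The case against.** A reader might infer that following either list necessarily loses RZV doses and places vaccinated people among the unvaccinated or 1-dose groups, and that VE is attenuated throughout. The protocol does not support that.
- It does not show that any dose is recorded only under a discordant code. Any dose billed under CPT 90750 is caught by both lists.
- The appendix describes the 828 codes as part two of a two-part product. The text-only 829 codes carry the same suffixes and may be the companion part. If so, the appendix list might lose no dose by omitting them. This is an inference, but it cannot be excluded.
- Attenuation is not the only possible direction, because misplaced 2-dose recipients could raise 1-dose VE.
- Section 6.1 cross-references the appendix, so the lists could be read together, and Section 2 makes the definition of code lists a step of data extraction.

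These points limit the likely harm and stand as far as that. They do not remove the contradiction: the lists differ, no rule of precedence is given, and the possible companion role of the 829 codes does not explain why the text omits two codes that the appendix labels Shingrix.

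**Conclusion.** The contradiction is certain and can be checked from the protocol alone: four of eight distinct NDCs stand in only one list. The consequence is conditional. Doses recorded only under a discordant NDC can be missed and can then misclassify exposure, dose number, index date, eligibility as a comparator and censoring.

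The number of such doses is unknown. For 2-dose VE, comparator contamination biases towards underestimation, and the loss is probably small: about 1 point at an assumed 5% contamination and about 2 points at 10%, when the true VE is 70%. This assumes that hidden vaccinees have full 2-dose protection and, for step 5, that they enter the matched set in proportion to the pool. Propensity matching to the closest comparators could select them more often. The figures do not cover misplaced index dates. For 1-dose VE the bias could go either way. The point is worth correcting because the definition is central and the correction is cheap; the protocol does not show that the primary results are in danger.

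**What to change.** Keep a single list in Section 13.4.3: the union of the eight NDCs in 11-digit format, each confirmed as an RZV product before the list is locked, plus CPT 90750. Replace the enumerations in Sections 5.2.1 and 6.1 with a reference to it, and limit the cross-reference in 6.1 to 13.4.3. State that the same list applies to dose 1, dose 2, dose 3, the no-previous-RZV exclusion and every censoring rule that depends on RZV.

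State which list produced the counts in Tables 2 and 3. A rerun of those tables is optional: the protocol already judges the Table 3 counts sufficient for 80% power at a VE of 50%, and a fuller list would be expected to raise them.

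The cost is a text edit, a check of eight codes and, if the cohorts have already been extracted with one of the shorter lists, one repeat extraction.

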#### 6.2. Other variables

Other variables will be identified from the OptumTM database and considered in the analyses when appropriate as covariates. A list of covariates to be included followed by a detailed description of covariates and sources is in section 6.3.

#### 6.3. Covariates of interest

Age in 5-year increments: 50-54, 55-59, 60-64, 65-69, 70-74, 75-79, ≥80 [Harpaz, 2019; Hayter, 2012; Johnston, 2009; Kawai, 2016; Marra, 2020; Tsai, 2017; Yun, 2016; Wallin, 2019; Weng, 2007; Yamaguchi, 2021].

Sex: female/male [Hayter, 2012; Johnson, 2015; Kawai, 2016; Marra, 2020; Tsai, 2017; Yamaguchi, 2021]

Race/ethnicity: Asian, Black, Hispanic, White, Multiple/Other/Unknown [Kawai, 2017a]. The definition of race/ethnicity will be further discussed in the SAP.

Use of AID-related medications: includes but not limited to: tofacitinib, biologics and conventional synthetic DMARD combination therapy, biologics (tumor necrosis factoralpha blockers), and disease-modifying antirheumatic drugs in the 365 days prior to the index date, as detailed in Appendix 4[Baumrin, 2019; Chakravarty, 2013; Khan, 2018; ILai, 2021; Marra, 2016; Yamaguchi, 2021].

Medical encounters: number of inpatient admissions in the 365 days prior to the index date (continuous), number of ambulatory visits in the 365 days prior to the index date (continuous), number of Emergency Department visits in the 365 days prior to the index date (categorized 0, 1, 2-3,  $\geq$ 4), number of rheumatologist outpatient visits (for SLE, RA, PsA) in the 365 days prior to the index date, number of dermatologists outpatient visits

219111 (EPI-ZOSTER-097 VE US DB)
Protocol Final

(for SLE, PsO) in the 365 days prior to the index date, number of neurologist outpatient visits (for SLE, MS) in the 365 days prior to the index date.

Healthcare cost level: categorized according to specific ith percentile in the 365 days prior to the index date. The definition of healthcare cost level will be further discussed in the SAP. Participants followed during the observation period without any claims reported will be considered as having a cost of \$0; if a participant has a negative estimated cost, the cost will be set to missing and the cost of all the unvaccinated matched participants will be set to missing also.

Presence of co-morbidities: kidney disease, cardiovascular disease, pulmonary disease [i.e., chronic obstructive pulmonary disease or chronic bronchitis, asthma], liver disease, diabetes mellitus, other autoimmune diseases, cancer, immunocompromising conditions [i.e., human immunodeficiency virus, cancer, transplant, immune-suppressive medications], SARS-CoV-2 infection/COVID-19 diagnosis with an index date after 2020) in the 365 days prior to the index date [Kawai, 2017a; Marra, 2020; Tsai, 2017; Yun, 2016].

Concomitant vaccinations during baseline: Influenza vaccine, tetanus, diphtheria and pertussis vaccine, pneumococcal vaccine in the 365 days prior to the index date, as a proxy for health behaviors.

Region of residence within U.S. as defined by the Census Bureau (4 regions: West, Midwest, South, Northeast) most recently prior to the index date [Izurieta, 2021; Sun, 2021].

Use of preventative services: screening, preventative visits in the 365 days prior to the index date [Izurieta, 2021].

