# 7.6. Matching

For the primary objectives, once sub-cohorts for each AID condition are identified, participants meeting inclusion criteria who receive 2 doses of RZV at least 28 days apart at the index date will be matched exactly with unvaccinated participants on age category by 5-year increments (50-54, 55-59, 60-64, 65-69, 70-74, 75-79, ≥80) and AID-related medication category (mutually exclusive) based on current use at the index date within the same AID group. Medication categories will be based on the medication windows described in 13.6. For the secondary objectives, participants meeting inclusion criteria who receive 1 dose of RZV at the index date will be matched with unvaccinated participants by 5-year increments (i.e., 50-54 age grouping) and by AID-related medication category (mutually exclusive) based on current use at the index date. Matching will be done with replacement.

Following matching as described above, propensity scores based on the likelihood of receiving RZV dose 2 versus no RZV vaccination will be calculated using logistic regression models with RZV vaccination as the dependent variable and independent variables as outlined in Section 6.2 to select the 3 unvaccinated participants which are the closest to each vaccinated participant, to reach a ratio of RZV vaccinated to RZV unvaccinated of 1:3. Propensity scores will be calculated within each cohort defined by AID to balance measured confounders (details to be provided in the SAP) among patients receiving RZV dose 2 and comparator patients with no prior RZV vaccination. A second cohort of patients will be created to compare patients receiving RZV dose 1 to patients with no prior vaccination, using the same approach to calculate propensity scores within each cohort defined by AID based on the likelihood of receiving RZV dose 1 versus no RZV vaccination. An unvaccinated patient may serve as a comparator for both the dose 1 and dose 2 cohorts, although separate index dates will be applied.

Covariate balance will be assessed before and after applying propensity scores using standardized mean differences, with standardized differences of 0.2 suggestive of important imbalance [Austin, 2009a; Austin, 2009b]. Any covariate demonstrating imbalance after weighting, suggesting residual confounding, will be included as an

219111 (EPI-ZOSTER-097 VE US DB)
Protocol Final

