#### 11.3.3. Descriptive analyses

The number and characteristics of participants in each cohort will be described and compared. Categorical variables such as gender will be presented as absolute numbers and percentages with p-values for the Pearson  $\chi^2$  test or Fisher's exact test, as appropriate. Continuous variables such as age in years will be presented as the mean with standard deviation and/or median with interquartile ranges, with p-values for the two-sample t-test or Wilcoxon rank-sum test, as appropriate. Absolute standardized differences will be calculated to assess the balance of covariates with a cut-off value of 0.20. Overall incidence rates of HZ for the 2-dose ( $\geq$ 28 days apart) and the 1-dose RZV vaccinated cohort and the matched unvaccinated cohort will be calculated by dividing the number of HZ cases by the total number of person-years.

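### Age enters the propensity score only in the bands already matched exactly, so age differences within bands (notably the open-ended ≥80 band) are not directly balanced, and the 0.20 rule is unlikely to prompt adjustment

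*Protocol*

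**What the plan says.** The age definition in Section 6.3 is "Age in 5-year increments: 50-54, 55-59, 60-64, 65-69, 70-74, 75-79, ≥80". No other form of age is listed. The same section marks inpatient admissions and ambulatory visits as continuous and puts emergency visits into categories. It leaves the definitions of race/ethnicity and cost level to the SAP, but not that of age.

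Section 7.6 has each vaccinee "matched exactly with unvaccinated participants on age category by 5-year increments (50-54, 55-59, 60-64, 65-69, 70-74, 75-79, ≥80" and on medication category. It then fits a logistic model for vaccination with "independent variables as outlined in Section 6.2", and uses the score to choose the three closest unvaccinated participants. Section 6.2 only points onward: "A list of covariates to be included followed by a detailed description of covariates and sources is in section 6.3".

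On balance, Section 7.6 treats "standardized differences of 0.2 suggestive of important imbalance". The sentence that begins "Any covariate demonstrating imbalance after weighting, suggesting residual confounding, will be included as an" goes on to place such a covariate in the Cox model. Section 11.3.3 repeats the 0.20 cut-off and also says: "Continuous variables such as age in years will be presented as the mean with standard deviation".

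**The concern.** The design has two stages: exact matching on coarse keys, then a propensity score to refine the choice within each cell. For age the second stage does nothing, because the score receives the same bands that define the cell. In a closed band the age difference within a matched set stays under 5 years. In the ≥80 band nothing limits it, so a vaccinee of 81 could be set against comparators of 90.

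The protocol treats age as important enough to match on exactly, and secondary objectives 3 to 9 stratify VE by age. If vaccinees and comparators differ in age within bands, part of that difference passes into the hazard ratio. The stated safeguard (adding an imbalanced covariate to the Cox model) acts only when the standardized difference is large.

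**Working it through.** The protocol gives no figure on this point to reproduce. The check has a textual part and an illustrative part.

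**1. What the age term does in the score.** Write the linear predictor for person i as b(band of i) + c′x(i), where x(i) holds the other covariates. Two people in the same exact-match cell share the band, so b(band) cancels from the difference between their linear predictors. It carries no information on age within the band.

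**2. What the balance check sees.** With three comparators per vaccinee drawn from the same band, the band distributions are identical. The standardized difference for banded age is then 0 by construction. For age in years, the 0.20 limit equals 0.20 × SD. The protocol gives no SD, so it was modelled from Table 1 (ages 50-59 / 60-69 / ≥70, for example RA 30.5 / 26.6 / 42.8% and MS 47.3 / 31.8 / 20.8%). Assumptions: age uniform within closed bands; those aged ≥80 make up 20 to 40% of those aged ≥70; an exponential tail capped at 90 years. Across RA, MS, SLE and IBD the SD is 9.0 to 10.9 years, so the limit is 0.2 × 9.0 = 1.8 to 0.2 × 10.9 = 2.2 years.

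A uniform 5-year band has an SD of 5/√12 = 1.44 years. A 2-year gap in every band would be 2/1.44 = 1.4 within-band SDs, which is a very large difference.

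**3. Assumed gaps carried through.** Overall shift = (share in closed bands × closed-band gap) + (share aged ≥80 × gap in ≥80). Example, RA with 20% of those ≥70 aged ≥80: 0.428 × 0.2 = 0.086 are aged ≥80, so gaps of 0.5 and 2 years give 0.914 × 0.5 + 0.086 × 2 = 0.63 years and a standardized difference of 0.63/10.0 = 0.063. HR factor = (1 + r)^(−shift), with an assumed rise r in HZ rate of 2 to 5% per year of age. Ranges over the four cohorts and both ≥80 shares, vaccinees younger:

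| Gap, closed / ≥80 (years) | Overall shift (years) | Standardized difference | HR factor |
|---|---|---|---|
| 0.25 / 1 | 0.28-0.38 | 0.031-0.035 | 0.982-0.994 |
| 0.5 / 2 | 0.56-0.76 | 0.061-0.070 | 0.964-0.989 |
| 1 / 3 | 1.08-1.34 | 0.116-0.124 | 0.937-0.979 |

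None reaches 0.20.

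**4. Effect on VE.** Observed VE = 1 − HR × (1 + r)^(∓shift), minus if vaccinees are younger and plus if older.

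| True VE | Shift, slope | Vaccinees younger | Vaccinees older |
|---|---|---|---|
| 50% | 0.6 y, 3% | 50.9% | 49.1% |
| 50% | 1.4 y, 5% | 53.3% | 46.5% |
| 70% | 0.6 y, 3% | 70.5% | 69.5% |
| 70% | 1.4 y, 5% | 72.0% | 67.9% |

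The 1.4 years is the largest modelled shift (1.34) rounded up.

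**The case against.** **The SAP.** Section 7.6 leaves propensity details to the SAP, and the functional form of a covariate is ordinary SAP content. This carries some weight, since a SAP could still enter age in years. But Section 6.3 states the form of age explicitly and does not defer it, although it defers two other variables. An analyst following the text would enter bands.

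**Detection.** A reader might infer that the balance check cannot detect a gap within bands. The protocol does not support that. Section 11.3.3 compares age in years with a test, in the same paragraph as the standardized differences. In RA, with 15,928 vaccinees (Table 3) and 47,784 comparators, an SD of 10 gives SE = 10 × √(1/15,928 + 1/47,784) = 0.091 years, ignoring replacement. A 0.4-year gap then has z of about 4.4 and would show. What remains is that a p-value triggers no adjustment, that 0.20 is too coarse to do so, and that the text does not say whether the standardized difference for age uses years or bands.

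**Balance.** Nor is it right that age within bands is never balanced. Comorbidities, encounters and cost are in the score and may balance age indirectly.

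**The oldest stratum.** If VE were reported for ≥80 alone, a 2-3 year gap and a slope of 2-4% per year would give factors of exp(−0.04) = 0.961 to exp(−0.12) = 0.887, and a true VE of 50% would read 52.0-55.7%. But no section defines ≥80 as a reporting stratum, and the age cut-points for objectives 3 to 9 are not stated. That figure cannot be presented as an expected bias.

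**Materiality.** At Table 2 and Table 3 values with a true VE of 50%, RA yields 15,928 × 1.4 × 0.01553 × 0.5 = 173 vaccinated events and 1,039 comparator events, for a 95% CI of about 41-57%. SLE yields about 32 and 193, for a CI of about 27-66%. One VE point is well inside that uncertainty. This stands, and it is why the point is minor.

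**Conclusion.** The point holds as a modest weakness in how age is specified. As written, the age term in the score cannot help select comparators, age within bands is not directly balanced, and the ≥80 band has no limit. A gap in age would be visible in the descriptive table but would rarely trigger adjustment.

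The size is about 1 VE point overall. Under the widest assumptions tried it is about 3.5 points at a true VE of 50% and about 2 points at 70%. The bias could go either way: nothing in the protocol shows that vaccinees would be the younger group within bands, so a claim that VE is overstated is not supported. The slope, the gaps, the share aged ≥80 and the SD are all assumptions. Table 1 describes all beneficiaries by age at diagnosis, not the matched cohorts. This is a desirable improvement and does not threaten the primary objectives.

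**What to change.** Keep the seven bands as the exact-matching key. In Sections 6.3 and 7.6, define age for the propensity model as age in years (linear plus a spline or quadratic term), and include age in years as a covariate in the Cox model whether or not the balance threshold is crossed. State in Sections 7.6 and 11.3.3 that the standardized difference for age is computed on age in years.

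Do not split the ≥80 matching band. That would change the matching key, thin the cells within each disease and medication category, and could leave vaccinees unmatched. Age in years deals with the open band without that loss.

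The cost is a few lines of text and a few model degrees of freedom. These are affordable even in SLE, with about 32 + 193 = 225 expected events under the assumptions above. No new data are needed, because Section 11.3.3 already uses age in years, and no participants are lost.
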